### 5.1.8.2 Toxicities during Maintenance or Consolidation Treatment

Guidelines for management of toxicities that occur during maintenance or consolidation treatment are presented in [Table 19](#).

**Table 19 Guidelines for Management of Toxicities That Occur during Maintenance or Consolidation Treatment**

Event	Action to Be Taken
Hematologic toxicity: Grade 3 or 4	

• Withhold study treatment.

• Administer myeloid growth factors for neutropenia as allowed according to institutional guidelines.

• Administer RBCs or platelets as required.

• If improvement to Grade <math>\leq 2</math>, resume obinutuzumab or rituximab at full dose and resume venetoclax at next lower dose for subsequent cycles per guideline in Section 5.1.8. Patients who are not eligible for further venetoclax dose reductions should be permanently discontinued.

• If study treatment is withheld for <math>> 42</math> days, permanently discontinue study treatment.

• Withdraw venetoclax and idasanutlin in case of recurrent episodes of Grade <math>\geq 3</math> thrombocytopenia and/or neutropenia.

Non-hematologic toxicity: Grade $\geq 2$	

• Withhold study treatment.

• If improvement to Grade <math>\leq 1</math> or baseline, resume obinutuzumab or rituximab at full dose and resume venetoclax at the next lower dose for subsequent cycles per guideline in Section 5.1.8. Patients who are not eligible for further venetoclax and/or idasanutlin dose reductions should be permanently discontinued.

• If study treatment is withheld for <math>> 42</math> days, permanently discontinue study treatment.

## 5.2 SAFETY PARAMETERS AND DEFINITIONS

Safety assessments will consist of monitoring and recording adverse events, including serious adverse events and adverse events of special interest, performing protocol-specified safety laboratory assessments, measuring protocol-specified vital signs, and conducting other protocol-specified tests that are deemed critical to the safety evaluation of the study.

Certain types of events require immediate reporting to the Sponsor, as outlined in Section [5.4](#).

### **5.2.1 Adverse Events**

According to the ICH guideline for GCP, an adverse event is any untoward medical occurrence in a clinical investigation subject administered a pharmaceutical product, regardless of causal attribution. An adverse event can therefore be any of the following:

- Any unfavorable and unintended sign (including an abnormal laboratory finding), symptom, or disease temporally associated with the use of a medicinal product, whether or not considered related to the medicinal product
- Any new disease or exacerbation of an existing disease (a worsening in the character, frequency, or severity of a known condition), except as described in Section [5.3.5.10](#)
- Recurrence of an intermittent medical condition (e.g., headache) not present at baseline
- Any deterioration in a laboratory value or other clinical test (e.g., ECG, X-ray) that is associated with symptoms or leads to a change in study treatment or concomitant treatment or discontinuation from study treatment
- Adverse events that are related to a protocol-mandated intervention, including those that occur prior to assignment of study treatment (e.g., screening invasive procedures such as biopsies)

### **5.2.2 Serious Adverse Events (Immediately Reportable to the Sponsor)**

A serious adverse event is any adverse event that meets any of the following criteria:

- Is fatal (i.e., the adverse event actually causes or leads to death)
- Is life threatening (i.e., the adverse event, in the view of the investigator, places the patient at immediate risk of death)

This does not include any adverse event that had it occurred in a more severe form or was allowed to continue might have caused death.

- Requires or prolongs inpatient hospitalization (see Section [5.3.5.11](#))
- Results in persistent or significant disability/incapacity (i.e., the adverse event results in substantial disruption of the patient's ability to conduct normal life functions)
- Is a congenital anomaly/birth defect in a neonate/infant born to a mother exposed to study treatment
- Is a significant medical event in the investigator's judgment (e.g., may jeopardize the patient or may require medical/surgical intervention to prevent one of the outcomes listed above)

The terms "severe" and "serious" are not synonymous. Severity refers to the intensity of an adverse event (e.g., rated as mild, moderate, or severe, or according to NCI CTCAE; see Section [5.3.3](#)); the event itself may be of relatively minor medical significance (such as severe headache without any further findings).

Severity and seriousness need to be independently assessed for each adverse event recorded on the eCRF.

Serious adverse events are required to be reported by the investigator to the Sponsor immediately (i.e., no more than 24 hours after learning of the event; see Section 5.4.2 for reporting instructions).

### **5.2.3 Adverse Events of Special Interest (Immediately Reportable to the Sponsor)**

Adverse events of special interest are required to be reported by the investigator to the Sponsor immediately (i.e., no more than 24 hours after learning of the event; see Section 5.4.2 for reporting instructions). Adverse events of special interest for this study include the following:

- Cases of potential drug-induced liver injury that include an elevated ALT or AST in combination with either an elevated bilirubin or clinical jaundice, as defined by Hy's Law (see Section 5.3.5.7)
- Suspected transmission of an infectious agent by the study treatment, as defined below

Any organism, virus, or infectious particle (e.g., prion protein transmitting transmissible spongiform encephalopathy), pathogenic or non-pathogenic, is considered an infectious agent. A transmission of an infectious agent may be suspected from clinical symptoms or laboratory findings that indicate an infection in a patient exposed to a medicinal product. This term applies only when a contamination of any of the study treatment components is suspected.

- TLS of any grade, irrespective of causality
- Grade  $\geq 3$  neutropenia, including febrile neutropenia
- Grade  $\geq 3$  thrombocytopenia or Grade  $\geq 2$  thrombocytopenia if associated with hemorrhage or bleeding)
- Grade 2 diarrhea
- Grade  $\geq 2$  *C. difficile* infection
- Second malignancies

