### 3.1.2.1 Definition of Dose-Limiting Toxicity

In this study, a DLT is defined as at least one of the following events occurring during the first two cycles of treatment and assessed by the investigator as clearly not related to the patient's underlying disease:

- Any Grade 5 adverse event unless unequivocally due to the underlying malignancy or extraneous causes
- Adverse event of any grade that leads to a delay of more than 14 days in the start of the next treatment cycle
- Hematologic adverse events that meet any of the following criteria:
  - Grade 3 or 4 neutropenia in the presence of sustained fever of  $>38^{\circ}\text{C}$  (lasting for  $>5$  days) or a documented infection
  - Grade 4 neutropenia lasting for  $>7$  days *despite adequate supportive care measures. G-CSF may be used to treat Grade  $\geq 3$  neutropenia but should not be used as prophylaxis in the DLT period.*
  - Grade 3 or 4 thrombocytopenia if associated with grade  $\geq 3$  bleeding
  - Grade 4 thrombocytopenia lasting for  $>7$  days
- Grade 3 or 4 non-hematologic adverse event, with the following exceptions:
  - Grade 3 or 4 IRRs
    - Note that IRRs are not dose-dependent events. They may occur even after a small amount of drug has been administered.
  - Grade 3 laboratory TLS without manifestations of clinical TLS (see [Appendix 5](#) for the Howard-based criteria for clinical and laboratory TLS)
  - Grade 3 AST or ALT increase lasting  $<7$  days
  - Grade 3 diarrhea that responds to adequate therapy within 48 hours

- Grade 3 nausea or vomiting that occurs in the absence of premedication and responds to adequate therapy within 72 hours
- Grade  $\leq 3$  fatigue, asthenia, anorexia, or constipation that resolves to Grade  $\leq 2$  in  $\leq 7$  days
- Any increase in hepatic transaminase  $> 3 \times$  baseline AND an increase in direct bilirubin  $> 2 \times$  ULN, WITHOUT any findings of cholestasis or jaundice or signs of hepatic dysfunction AND in the absence of other contributory factors (e.g., worsening of metastatic disease or concomitant exposure to known hepatotoxic agent or of a documented infectious etiology) is suggestive of potential drug induced liver injury (DILI) (according to Hy's Law) and will be considered a DLT.

Other toxicities that are considered clinically relevant and related to study treatment as determined by the investigator and the Medical Monitor may also be considered DLTs.

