## **5.4 IMMEDIATE REPORTING REQUIREMENTS FROM INVESTIGATOR TO SPONSOR**

Certain events require immediate reporting to allow the Sponsor to take appropriate measures to address potential new risks in a clinical trial. The investigator must report such events to the Sponsor immediately; under no circumstances should reporting take place more than 24 hours after the investigator learns of the event. The following is a list

of events that the investigator must report to the Sponsor within 24 hours after learning of the event, regardless of relationship to any of the study treatments:

- Serious adverse events (see Section 5.4.2 for further details)
- Adverse events of special interest (see Section 5.4.2 for further details)
- DLTs (see Section 5.4.2 for further details)
- Pregnancies (see Section 5.4.3 for further details)
- *Overdoses, medication errors, drug abuse, or drug misuse (see Section 5.4.4 for details on reporting requirements)*

The investigator must report new significant follow-up information for these events to the Sponsor immediately (i.e., no more than 24 hours after becoming aware of the information). New significant information includes the following:

- New signs or symptoms or a change in the diagnosis
- Significant new diagnostic test results
- Change in causality based on new information
- Change in the event's outcome, including recovery
- Additional narrative information on the clinical course of the event

Investigators must also comply with local requirements for reporting serious adverse events to the local health authority and IRB/EC.

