### **6.2.2 Selected AEs and AE of Special Interest (AESI)**

Selected AE and AESI were defined based on the clinical experience with study treatment components that represent an IMP. Also anticipated potentially overlapping toxicities as specified in respective study protocols need to be taken into account.

Definitions for selected AE and AESI are provided in subsequent tables.

Selected AE Category	Definition	BO29563	BO29562	BO29561	BH29812	BH39147	GO29833	GO29834
Thrombocytopenia	SMQ "HAEMATOPOIETIC THROMBOCYTOPENIA narrow" (20000031n)	x	x	x	x	x	x	x
Hepatitis B reactivation/newly occurring	PT 'HEPATITIS B'	x	x	x	x	x	x	x
Cardiac AE	SOC "CARDIAC DISORDERS"	x	x	x	x	x	x	x
Infusion Related Reaction (IRR)	PT 'INFUSION RELATED REACTION' and related to at least one component of study treatment and event occurred within 24 hours or during infusion and tickbox 'Systemic Infusion Reaction' ticked (This definition was applied in BO29563- study lead BioStats/SPA please check if this is valid for your study)	x	x	x	x	x	x	x
Infections	SOC 'INFECTIONS AND INFESTATIONS'	x	x	x	x	x	x	x
Neutropenia	Roche Standard AEGT "NEUTROPENIA AND ASSOCIATED COMPLICATIONS" (for BO29561-3: including late onset and prolonged neutropenia) (SMQ Haematopoietic leukopenia narrow for GO29833/834)	x	x	x	x	x	x	x

Selected AE Category	Definition	BO29563	BO29562	BO29561	BH29812	BH39147	GO29833	GO29834
Prolonged neutropenia	Initial ANC < 1.0 × 10  /L that is still present 28 days after treatment with GA101				x	x		
Late onset Neutropenia	ANC < 1.0 × 10  /L occurring ≥ 28 days after ga101 infusion has been completed/stopped				x	x		
Gastrointestinal perforation	SMQ "GASTROINTESTINAL PERFORATION" (20000107 narrow).	x	x	x	x	x	x	x
Peripheral Neuropathy (motor/and or sensory)	SMQ Peripheral neuropathy wide			x			x	x
Dose Limiting Toxicity	CRF tickbox				x			
Drug-drug interactions	Single PT		x					

AE of Special Interest	Definition	BO29563	BO29562	BO29561	BH29812	BH39147	GO29833	GO29834
Drug induced liver injury	<del>Respective tickbox for AESI on CRF page ticked</del>				x	x	x	x
Suspected transmission of infectious agent	<del>Respective tickbox for AESI on CRF page ticked</del>				x	x	x	x
Grade 4 thrombocytopenia	SMQ "HAEMATOPOIETIC THROMBOCYTOPENIA narrow" (20000031n)						x	
Grade ≥ 3 infection	SOC						x	
Grade ≥ 3 thrombocytopenia or Grade 2 thrombocytopenia if associated with hemorrhage/bleeding	?				x	x		
Grade ≥ 2 diarrhea	?				x	x		

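### Protocol makes only Grade 2 diarrhea an immediately reportable AESI while the SAP uses Grade 2 or higher, so some non-serious Grade 3 diarrhea escapes the 24-hour rule

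*Protocol*

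**What the plan says.** Protocol Section 5.2.3 sets the duty: "Adverse events of special interest are required to be reported by the investigator to the Sponsor immediately", with a limit of 24 hours after learning of the event. Its list of AESIs includes "Grade 2 diarrhea", with no sign or words extending it to higher grades. The other entries with a grade limit all set a floor: neutropenia from Grade 3, thrombocytopenia from Grade 3 (or from Grade 2 with bleeding), and *C. difficile* infection from Grade 2. Tumor lysis syndrome is included at any grade.

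SAP Section 6.2.2 has a row "Grade ≥ 2 diarrhea" in its AESI table, marked for BH39147. The cell that should hold the search definition contains only a question mark.

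Protocol Section 5.4 gives the other 24-hour routes. Those that matter here are serious adverse events (SAEs) and DLTs. Section 6.4 commits the Sponsor to summarizing and listing all AESIs, so the definition governs an analysis output as well as a reporting duty.

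**The concern.** A reporting list should not capture a mild form of a toxicity and omit a worse form. A site that follows Section 5.2.3 to the letter reports a Grade 2 episode within 24 hours. It commits no deviation if it handles a non-serious Grade 3 episode as an ordinary adverse event.

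The toxicity matters in this trial. Section 5.1.3.1 calls diarrhea the most common adverse event with idasanutlin, Section 1.3.2 reports Grade 3 diarrhea as a DLT on the daily × 5 schedule, and Section 5.1.5 names diarrhea as an overlapping toxicity of the obinutuzumab triplet.

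There is also an analysis consequence. The protocol's AESI set for diarrhea is Grade 2 alone and the SAP's is Grade 2 and above. A table programmed from one document will not agree with a reconciliation made from the other.

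**Working it through.** The plan gives no figure to reproduce. The check is a comparison of text followed by a rough size.

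**Step 1: is another 24-hour route open for each kind of event?**

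| Diarrhea event | Route | Due within 24 hours? |
|---|---|---|
| Grade 2 | AESI, Section 5.2.3 | Yes |
| Any grade, serious | SAE, Sections 5.2.2 and 5.4 | Yes |
| Grade 4 | SAE if life-threatening. Table 20, footnote d, also sends Grade 4 events to SAE reporting, although that table is for events that CTCAE does not list | In practice yes |
| Grade 4, or Grade 3 not responding within 48 hours, in Cycles 1–2 of dose escalation | DLT, Sections 3.1.2.1 and 5.4, if the rest of the DLT definition is met | Yes |
| Grade 3 that was first reported at Grade 2 | Already an AESI. Section 5.4 requires significant follow-up within 24 hours | Yes |
| Non-serious Grade 3 in the DLT window, responding within 48 hours | None | **No** |
| Non-serious Grade 3 in later escalation cycles, post-induction treatment or the expansion phase | None | **No** |

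Three points support the last two rows.

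- The DLT definition takes in a "Grade 3 or 4 non-hematologic adverse event, with the following exceptions", and one of those exceptions is "Grade 3 diarrhea that responds to adequate therapy within 48 hours". Section 4.4.2 places the DLT window in the first two cycles of the escalation phase, so the DLT route does not exist in expansion.
- Section 5.2.2 separates severity from seriousness and requires each to be judged independently. Grade 3 alone does not make an event an SAE.
- Section 5.2.4 does not list diarrhea among the selected adverse events.

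**Step 2: how many patients?** Inputs are Table 13 (Grade 3 or higher diarrhea in 8% of 38 patients on idasanutlin alone and 3% of 128 on venetoclax alone) and Section 6.1.2 (80 expansion patients).

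Number affected = N × p × (1 − s) × (1 − r), where p is the Grade 3 or higher rate, s the fraction that are serious, and r the fraction of the rest already reported at Grade 2.

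- With s = r = 0: 80 × 0.03 = 2.4 and 80 × 0.08 = 6.4, so about 2 to 6 patients.
- With s = 1 or r = 1: 0 patients.

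The documents give neither s nor r. At single-agent rates the range in expansion is therefore 0 to about 6. The rate with the triplet is not known and may differ.

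**The case against.** The best case on the other side is that this is a single missing symbol. The neighbouring bullets carry the sign, the SAP carries it for this item, and the intent is easy to guess. That is fair as to cause, but sites work from the protocol as written. Loss of one sign when the PDF was converted to text is unlikely, because four such signs survive in the same list, including those in the bullets directly above and below. It cannot be fully excluded. If the PDF itself shows the sign, the grade mismatch disappears.

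The objection also limits how far the point reaches. A reader might infer four stronger things that the documents do not support.

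- *That all non-serious Grade 3–4 diarrhea goes unreported.* The SAE, DLT and follow-up routes cover much of it, and non-serious Grade 4 diarrhea is close to an empty category.
- *That the internal monitoring committee would miss these events.* Nothing makes AESI reports its source. Under Section 3.1.4 the investigator and Medical Monitor assess adverse events continually, Grade 3 and above in particular, and the committee reviews cumulative data. Under Section 5.3.1 every adverse event is entered on the eCRF.
- *That expedited reporting is affected.* The protocol uses that term in Section 5.7 for the Sponsor's reports to authorities, investigators and ethics bodies. The duty here is the investigator's immediate report to the Sponsor.
- *That 4 to 11 of 140 patients are affected* (140 × 0.03 = 4.2; 140 × 0.08 = 11.2). That is a gross count of all Grade 3 or higher diarrhea, before removing events with another 24-hour route.

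Finally, no severity analysis is lost: SAP Outputs 30, 38 and 50 list and tabulate Grade 3–5 events separately. The SAP row is itself unfinished, and the SAP introduction does not list BH39147. Both facts weaken the SAP as a reference but do not remove the disagreement.

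**Conclusion.** The inconsistency is real and its consequence is narrow. As written, the protocol leaves outside immediate reporting to the Sponsor the non-serious, non-DLT Grade 3 diarrhea that was not already reported at Grade 2, while Grade 2 diarrhea is inside. The two documents also define different AESI sets. The effect is delayed notification and inconsistent counts; the events themselves are not lost.

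The size of 2 to 6 expansion patients is a figure before exclusions, not an estimate of the number affected. It assumes that single-agent rates carry over to the triplet. The 8% rests on about 3 patients (0.08 × 38 = 3.04) with solid tumors, in a group where 20 were treated above the maximum tolerated dose. The finding assumes that the PDF shows the protocol entry without the sign. It is worth correcting because it sits in a rule that sites must follow, for a leading toxicity of the regimen.

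**What to change.** Reconcile Protocol Section 5.2.3 and SAP Section 6.2.2 to one AESI definition for diarrhea, stated as a minimum grade like the other graded entries, after checking the PDF. In the SAP, replace the question mark in the definition cell with the matching search definition so that the row can be programmed. Add BH39147 to the studies named in the SAP introduction.

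The cost is one symbol in the protocol at the next amendment, a matching line in the site reporting instructions and two small SAP edits. No design element, sample size or efficacy analysis changes. Sites would send the Sponsor a few more immediate reports.

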### **5.2.4 Selected Adverse Events**

Selected adverse events in this study are defined as adverse events for which additional data collection or analyses will be performed. Selected adverse events do not require immediate reporting if they are not serious or meet the adverse events of special interest definition (see Section 5.2.3).

The following adverse events are considered selected adverse events:

- Thrombocytopenia, including acute thrombocytopenia (events occurring during and within 24 hours following an obinutuzumab infusion)

- Hepatitis B reactivation
- Cardiac events
- TLS
- IRRs
- All infections, including PML
- Neutropenia, including prolonged neutropenia (neutropenia < 1000 cells/ $\mu$ L that does not resolve after 28 days without obinutuzumab treatment) and late-onset neutropenia (neutropenia < 1000 cells/ $\mu$ L occurring  $\geq$  28 days after obinutuzumab treatment has been completed or stopped)
- GI perforation

Events for which additional data collection will be required are PML and hepatitis B reactivation.

### **5.3 METHODS AND TIMING FOR CAPTURING AND ASSESSING SAFETY PARAMETERS**

The investigator is responsible for ensuring that all adverse events (see Section 5.2.1 for definition) are recorded on the Adverse Event eCRF and reported to the Sponsor in accordance with instructions provided in this section and in Sections 5.4–5.6.

For each adverse event recorded on the Adverse Event eCRF, the investigator will make an assessment of seriousness (see Section 5.2.2 for seriousness criteria), severity (see Section 5.3.3), and causality (see Section 5.3.4).

#### **5.3.1 Adverse Event Reporting Period**

Investigators will seek information on adverse events at each patient contact. All adverse events, whether reported by the patient or noted by study personnel, will be recorded in the patient's medical record and on the Adverse Event eCRF.

**After informed consent** has been obtained **but prior to initiation of study treatment**, only serious adverse events caused by a protocol-mandated intervention (e.g., invasive procedures such as biopsies, discontinuation of medications) should be reported (see Section 5.4.2 for instructions for reporting serious adverse events).

**After initiation of study treatment**, all adverse events will be reported until 90 days after the last dose of study treatment, and Grade 3 or 4 infections (related and unrelated) in patients who received obinutuzumab will continue to be reported until up to 2 years after the last dose of obinutuzumab.

Second malignancies will be recorded indefinitely for patients who received obinutuzumab (even if the study has been closed) (see Section 5.6).

Instructions for reporting adverse events that occur after the adverse event reporting period are provided in Section 5.6.

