### **5.1.1.5 Infections**

On the basis of its mechanism of action, resulting in profound B-cell depletion, obinutuzumab may be associated with an increased risk of infections. Obinutuzumab should not be administered to patients with active infection, and caution should be exercised when including patients with a history of recurrent or chronic infections.

Serious bacterial, fungal, and new or reactivated viral infections can occur during and following the completion of obinutuzumab therapy. Fatal infections have been reported.

Reactivation of hepatitis B in patients with chronic hepatitis (HBsAg positive) with evidence of prior hepatitis B exposure, or in patients who are carriers (HBsAg negative and HBcAb positive) has been reported with other anti-CD20 antibodies. The risk is increased particularly when anti-CD20 antibodies are administered with immunosuppressive therapies, such as steroids or chemotherapy. Particular attention should be given to patients who have previously received highly immunosuppressive treatment, such as high-dose chemotherapy and SCT. Patients positive for HBsAg and HBcAb are not eligible for this study.

John Cunningham (JC) viral infection resulting in PML has been reported in patients treated with obinutuzumab. The diagnosis of PML should be considered in any patients presenting with new-onset neurologic manifestations. The symptoms of PML are unspecific and can vary, depending on the affected region of the brain. Motor symptoms with corticospinal tract findings (e.g., muscular weakness, paralysis, and sensory disturbances), sensory abnormalities, cerebellar symptoms, and visual field defects are common. Some signs or symptoms regarded as “cortical” (e.g., aphasia or visual-spatial disorientation) may occur. Evaluation of PML includes, but is not limited to, consultation with a neurologist, brain MRI, and lumbar puncture (cerebrospinal fluid testing for JC viral DNA). Additional guidelines for medical management of PML in this study are provided in [Table 19](#).

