#### **5.1.2.2 Infections (Including Serious Infections)**

Serious infections, including fatal bacterial, fungal, and new or reactivated viral infections, can occur during and up to 1 year following completion of rituximab-based therapy.

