#### **5.1.2.4 Progressive Multifocal Leukoencephalopathy**

Rare cases of PML have also been reported in patients treated with rituximab alone or in combination with other immunosuppressive medications ([Goldberg et al. 2002](#); [Calabrese et al. 2007](#); [Carson and Bennett 2009](#)). In a review of 57 patients who developed PML after rituximab administration, all patients had received prior therapies with alkylating agents, corticosteroids, purine analogs, or drugs to prevent allogeneic stem cell or solid-organ graft rejection. The diagnosis of PML in any patient treated with rituximab is rare, but it should be suspected in any patient who develops new-onset neurologic manifestations. The majority of patients with hematologic malignancies diagnosed with PML received rituximab in combination with chemotherapy or as part of a hematopoietic SCT. Most cases of PML were diagnosed within 12 months of the patients' last infusion of rituximab.

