### **5.6 ADVERSE EVENTS THAT OCCUR AFTER THE ADVERSE EVENT REPORTING PERIOD**

After the end of the adverse event reporting period (defined as 90 days after the last dose of study drug), all deaths, regardless of cause, should be reported on the Long-Term Survival Follow-Up eCRF. Grade 3 and 4 infections (related and unrelated) in patients who received obinutuzumab should be reported on the Adverse Event eCRF until up to 2 years after the last dose of obinutuzumab. In addition, if the investigator becomes aware of a serious adverse event that is believed to be related to prior study treatment, the event should be reported through use of the Adverse Event eCRF. The sponsor should also be notified of events of second malignancies indefinitely (even if the study has been closed) for patients who received obinutuzumab.

The investigator should report any other events (excluding related serious adverse events 90 days after the last dose of study treatment if the investigator becomes aware of any event and Grade 3 and 4 infections, independently of causality, for 2 years) directly to the Sponsor or its designee, either by faxing or by scanning and emailing the Serious Adverse Event/Adverse Event of Special Interest Reporting Form using the fax number or email address provided to investigators.

During survival follow-up, deaths attributed to progression of lymphoma should be recorded only on the Study Completion/Early Discontinuation eCRF.

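### After day 90, infections in rituximab-treated DLBCL patients must go on the AE eCRF only if serious, believed related and known to the investigator, although the protocol puts the serious-infection risk at up to 1 year

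*Protocol*

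**What the plan says.** **Reporting rules.** Protocol 5.3.1 requires all adverse events to be reported until 90 days after the last dose of study treatment. The infection exception is tied to obinutuzumab: "Grade 3 or 4 infections (related and unrelated) in patients who received obinutuzumab will continue to be reported until up to 2 years". That period is counted from the last dose of that antibody. Section 5.6 and Appendix 2 footnote ee carry the same limit.

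For anyone outside the exception, 5.6 asks for an AE eCRF entry after day 90 "if the investigator becomes aware of a serious adverse event that is believed to be related to prior study treatment". For deaths it says that "all deaths, regardless of cause, should be reported on the Long-Term Survival Follow-Up eCRF".

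Section 5.6 also has a catch-all: "The investigator should report any other events (excluding related serious adverse events 90 days after the last dose of study treatment", with a further exclusion that reads "Grade 3 and 4 infections, independently of causality, for 2 years) directly to the Sponsor or its designee". The route is the SAE/AESI form, sent by fax or email.

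**Risk statements.** For rituximab, 5.1.2.2 says serious infections, fatal ones included, "can occur during and up to 1 year following completion of rituximab-based therapy". Section 5.1.2.4 adds: "Most cases of PML were diagnosed within 12 months of the" last rituximab infusion. For obinutuzumab, 5.1.1.5 says: "Serious bacterial, fungal, and new or reactivated viral infections can occur during and following the completion of obinutuzumab therapy".

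**The concern.** The protocol warns of late infection with both antibodies, but only obinutuzumab patients have late severe infections collected on the AE eCRF whatever the investigator thinks of causality. The rituximab patients are the DLBCL bridging cohorts, whose size is not fixed, and about 40 DLBCL expansion patients. DLBCL patients given obinutuzumab in early dose escalation are covered by the exception and are not part of this point.

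Safety is a primary objective of the expansion phase, and the study has no randomized control. Infection is a listed overlapping toxicity of rituximab, idasanutlin and venetoclax (Protocol 5.1.5, Table 14), and 5.1.3.3 concedes that causality of infections under idasanutlin can be hard to judge. A late-infection summary built from the AE eCRF would therefore include only events that investigators attributed to treatment. SAP 6.2.2 lists infections as a selected adverse event for this study, and SAP 6.2.1 puts no upper time limit on follow-up-period tables, so such a summary is possible.

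**Working it through.** There is no planned figure to reproduce. The check sets the reporting routes side by side and then takes one difference in days.

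**Routes for an infection starting more than 90 days after the last study dose** (Protocol 5.3.1, 5.6, Appendix 2 footnote ee)

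| Infection | Received obinutuzumab | Received rituximab |
|---|---|---|
| Serious, believed related, known to investigator | AE eCRF | AE eCRF |
| Grade 3 or 4, judged unrelated | AE eCRF, up to 2 years after last obinutuzumab dose | Not AE eCRF; perhaps SAE/AESI form |
| Grade 3, related but not serious | AE eCRF, same window | Not AE eCRF; perhaps SAE/AESI form |
| Fatal | Recorded as a death | Recorded as a death |

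The antibodies differ in the two middle rows, mainly the first of them.

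**The catch-all in 5.6 has two readings.**

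1. Its parenthesis removes events that 5.6 has already sent to the AE eCRF, that is, the obinutuzumab infections. Rituximab infections then count as other events and go to the Sponsor on the form. This is the more natural reading.
2. Its parenthesis names no antibody, so it removes all Grade 3 and 4 infections. Those judged unrelated in rituximab patients then have no stated route.

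On neither reading do they reach the AE eCRF, and footnote ee does not contain the catch-all. The opening of 5.3.1, on recording all adverse events, is limited by the 90-day rule that follows it.

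**Length of the gap on the AE eCRF**

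- Inputs: a 1-year risk window, 365 days (5.1.2.2), and a 90-day reporting window (5.3.1).
- Assumption: the last dose of study treatment marks completion of rituximab-based therapy.
- 365 − 90 = 275 days; 275 / 365 = 75%.

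If the risk year is counted from the last rituximab dose and oral dosing ends g days later, the gap is 275 − g. For a patient who stops after a full last induction cycle, rituximab is given on Day 1 and the oral drugs end on Day 5 or Day 10. Then g is 4 or 9, and the gap is 271 or 266 days. In consolidation g is not fixed, because the Sponsor sets the oral regimen later.

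**Events affected.** The documents give no late-infection rate, so the number cannot be calculated.

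**The case against.** The case against is substantial.

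- **The limit looks deliberate.** It is worded consistently in 5.3.1, 5.6 and the schedule footnotes, and indefinite second-malignancy reporting is also confined to obinutuzumab. Nothing requires the collection window to match the risk window. This stands: the point is a design choice that could be improved, not an error.
- **The Sponsor probably hears of these events anyway.** A reader might infer that late infections in rituximab patients go unreported for 275 days. The documents do not support that. On its natural reading, the catch-all sends them to the Sponsor with no causality filter. The 275 days apply to the AE eCRF only.
- **What remains is small.** Serious infections attributed to treatment are captured, and so are deaths. An investigator is unlikely to call late PML unrelated when 5.1.2.4 describes the link, so PML adds little weight.
- **A contrast with FL is weak.** A reader might infer a biased comparison of 2 years in FL with 90 days in DLBCL. No such comparison is planned; expansion data are summarized by histology. The 2 years are also nominal, because under 3.2 the study may close once FL patients have finished treatment and DLBCL patients have 1 year of follow-up.
- **No affected table can be shown.** The shells for SAP Outputs 36 and 37 stop at an unspecified number of days after the last dose, and the List of Planned Outputs is not available. Output 36 note 4 gives the 2-year infection exception without naming an antibody, but it is a multi-study shell and sets no duty for sites.

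The answer to all of these is narrow: safety forms are not the AE eCRF, and the sentence that would carry these events can be read as excluding them.

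**Conclusion.** The point holds as a low-severity, cheap improvement. In rituximab-treated DLBCL patients, the AE eCRF after day 90 is required to hold only infections that are serious, believed related and known to the investigator, for 275 of the 365 days (75%) in which 5.1.2.2 says serious infections can occur. Any late-infection summary drawn from it would be filtered by causality judgment.

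This rests on taking the last study dose as completion of rituximab-based therapy; counting from the last rituximab dose shortens the gap. The number of events affected is unknown. The primary endpoint, DLT decisions, treatment-period tables (which end 28 days after the last dose, or earlier if new therapy starts) and death capture are unaffected.

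**What to change.** 1. In Protocol 5.3.1, 5.6 and Appendix 2 footnote ee, require Grade 3 to 5 infections (related and unrelated, including PML) on the AE eCRF for 12 months after the last dose of study treatment in patients who received rituximab. Collect them at the existing 3-monthly post-treatment visits, ending at progression, new anti-lymphoma therapy or transplant.
2. Reword the catch-all in 5.6 so that each infection rule names its antibody and its window.

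**Cost.** This is wording for the next amendment, with the approvals that 9.6 requires. Progression-free DLBCL patients are already assessed every 3 months (3.1.6), the study stays open until DLBCL patients have at least 1 year of follow-up (3.2), and adverse events are asked about at each contact (5.3.1). The burden is a few extra AE forms. The limitation is that nothing is covered after progression or new therapy. Extending it there would need new data collection, because those contacts now cover only survival and new treatment, and that would not clearly be cheap.
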